4.1. Primary Efficacy Endpoint

The primary efficacy endpoint is the change in the Yale Global Tic Severity Scale – Total Tic Score (YGTSS-TTS, i.e., sum of the motor and phonic tic scores) from baseline (YGTSS-TTS score from Baseline visit) to end of therapy (YGTSS-TTS score from Week 12).

4.1.1. Primary Efficacy Estimand

The mean change from baseline in the Yale Global Tic Severity Scale – Total Tic Score to end of therapy are compared between ecopipam and placebo for patients aged 6 to less than 18 years eligible for the trial.

The primary estimand is defined as the following:

Treatment: 4-week titration period followed by 8-week treatment phase with ecopipam HCI doses or matching placebo.

Target Population: all children and adolescent patients with Tourette's syndrome who were randomized, received at least one dose of study drug, and had at least one post Baseline scoring of the YGTSS (mITT population).

Variable: the change in the Yale Global Tic Severity Scale (YGTSS) from baseline to Week 12.

Intercurrent events: For the intercurrent events, receiving prohibited concomitant medication, change in dosing of allowed concomitant medication, and no dosing adjustment with BMI change, the treatment policy strategy will be used for the primary analysis, meaning the observed data at Week 12 will be used for the change from baseline in YGTSS. For the intercurrent event of study treatment discontinuation due to lack of efficacy and treatment related adverse events, for subjects with no YGTSS at Week 12, the hypothetical strategy will be used, meaning the non-collected data of YGTSS at Week 12 will be multiple imputed using similar subjects (relevant demographic/baseline characteristics) from the placebo arm. The intercurrent event 'death prior to Week 12' will be handled using the 'while alive and on-treatment strategy' using the last observed YGTSS assessment for the analysis of Week 12.

Population-level summary: treatment difference between ecopipam and placebo treatment groups using MMRM model in mITT population after having applied the hypothetical strategy and the while-on-treatment strategy, respectively, to the non-collected / non-observed Week 12 YGTSS assessments specified above.

The primary efficacy analysis approach is in line with the primary estimand. Potential confounders will be identified and sensitivity and/or supplementary analysis may be used to deal with missing data and assess the robustness of conclusions.

4.2. Secondary Efficacy Endpoints

Key Secondary Efficacy Endpoint:

 Change in Clinical Global Impression of Tourette Syndrome Severity (CGI-TS-S) from Baseline to Week 12

Other Secondary efficacy endpoints include:

- Change in Clinician Global Impression Tourette Syndrome of Improvement (CGI-TS-I) from Week 4 to Week 12
- Change in YGTSS-Global Score (GS) from Baseline to Week 12
- Change in Caregiver Global Impression of Change (CaGI-C) from Week 4 to Week 12
- Change in Gilles de la Tourette Syndrome–Quality of Life Scale for Children and Adolescents (C&A-GTS-QOL) from Baseline to Week 12
- Percentage of subjects with a 25%, 50%, and 75% improvement on the YGTSS-TTS
- Percentage of subjects with complete remission of tics on the YGTSS-TTS (100% improvement)
- Change in YGTSS-TTS from Baseline to Weeks 4, 6, and 8
- Change in CGI-TS-S from Baseline to Weeks 4, 6, and 8
- Change in CGI-TS-I from Baseline to Weeks 4, 6, and 8
- Change in YGTSS-GS from Baseline to Weeks 4, 6, and 8
- Change in CaGI-C from Baseline to Weeks 4, 6, and 8
- Change in the C&A-GTS-QOL from Baseline to Weeks 4, 6, and 8.

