11.2. Secondary Efficacy Assessments

Key Secondary Efficacy Endpoint:

• Change in Clinical Global Impression of Tourette Syndrome Severity (CGI-TS-S) from Baseline to Week 12

Other Secondary efficacy endpoints include:

- Change in Clinician Global Impression Tourette Syndrome of Improvement (CGI-TS-I) from Week 4 to Week 12
- Change in YGTSS-Global Score (GS) from Baseline to Week 12
- Change in Caregiver Global Impression of Change (CaGI-C) from Week 4 to Week 12
- Change in Gilles de la Tourette Syndrome–Quality of Life Scale for Children and Adolescents (C&A-GTS-QOL) from Baseline to Week12
- Percentage of subjects with a 25% improvement on the YGTSS-TTS
- Percentage of subjects with complete remission of tics on the YGTSS-TTS
- Change in YGTSS-TTS from Baseline to Weeks 4, 6, and 8
- Change in CGI-TS-S from Baseline to Weeks 4, 6, and 8
- Change in CGI-TS-I from Baseline to Weeks 4, 6, and 8
- Change in YGTSS-GS from Baseline to Weeks 4, 6, and 8
- Change in CaGI-C from Baseline to Weeks 4, 6, and 8

• Change in the C&A-GTS-QOL from Baseline to Weeks 4, 6, and 8

Rank order of hierarchy of the secondary endpoints will be outlined in the statistical analysis plan.

The CGI consists of two reliable and valid 7-item Likert scales used to assess severity and change in clinical symptoms. The improvement scale will be used at every visit after the Screening and Baseline Visits. The scale ranges from 1 = "very much improved" to 7 = very much worse." The CGI severity scale will be used at each study site visit and ranges from 1 = "not ill at all" to 7 = "among the most extremely ill."

Gilles de la Tourette Syndrome–Quality of Life Scale for Children and Adolescents (C&A-GTS-QOL) is a patient-reported health related quality of life measure developed for children and adolescents.

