Summary statistics will be presented along with a full data listing by treatment group.

8.2.2. Change in Clinician Global Impression Tourette Syndrome of Improvement (CGI-TS-I) from Baseline to Week 12

The CGI consists of two reliable and valid 7-item Likert scales used to assess severity and change in clinical symptoms. The improvement scale (CGI-TS-I) will be used at every visit after the Screening and Baseline Visits. The scale ranges from 1 = "very much improved" to 7 = very much worse." The CGI severity scale (CGI-TS-S) will be used at each study site visit and ranges from 1 = "not ill at all" to 7 = "among the most extremely ill."

A secondary analysis will be performed on the CGI-TS-I at Week 12.

Statistical analysis:

The analysis method will be the same as the primary efficacy analysis as described in **Section 8.1.1**, with the exception of no baseline score will be used as a covariate.

Summary statistics will be presented along with a full data listing by treatment group.

8.2.3. Change in YGTSS-Global Score (GS) from Baseline to Week 12

A secondary analysis will be performed on the change in YGTSS-Global Score (YGTSS-GS) from Baseline to Week 12.

Statistical analysis:

The analysis method will be the same as the primary efficacy analysis as described in Section 8.1.1.

Summary statistics will be presented along with a full data listing by treatment group.

8.2.4. Change in Caregiver Global Impression of Change (CaGI-C) from Baseline to Week 12

The CaGI-C scale is a 7 point Likert scale that asks the caregiver the following question: overall, how have the patient's symptoms changed (if at all) since the beginning of the study (before starting treatment)? The CaGI-C is rated as follows: 1 (very much improved), 2 (much improved), 3 (minimally improved), 4 (no change), 5 (minimally worse, 6 (much worse), and 7 (very much worse).

A secondary analysis will be performed on the change in CaGI-C from Baseline to Week 12.

Statistical analysis:

The analysis method will be the same as the primary efficacy analysis as described in **Section 8.1.1**, with the exception of no baseline score will be used as a covariate.

Summary statistics will be presented along with a full data listing by treatment group.

8.2.5. Change in Gilles de la Tourette Syndrome – Quality of Life Scale for Children and Adolescents (C&A-GTS-QOL) from Baseline to Week 12

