The condition power will then be calculated under the following for the treatment difference δ and standard error $Var(\hat{\delta}_1)$:

3) Using the estimates from the stage 1 data. Treatment difference δ is the Stage 1 MMRM treatment effect (δ₁) and Var(δ₁) is the variance of this estimate of treatment difference based on the covariance matrix of the LSmeans.

Using these results, the DSMB may make one of the following recommendations:

- If the conditional power at the planned sample size (150) is less than 30% then the DSMB may recommend that the study be terminated for futility.
- 2) If the conditional power at the planned sample size (150) is greater than 30% and less than 80%, then the planned sample size will be increased up to 200 to try to achieve a conditional power of at least 80%. If the conditional power at the maximum sample size (200) is still less than 80%, the DSMB may recommend continuing the study at the maximum sample size (200).
- If the conditional power is at least 80%, then the DSMB may recommend continuing this study with the planned sample size (150).

Full details of the DSMB including primary responsibilities, its relationship with other study components, its membership, and the purpose and timings of its meetings are documented in a DSMB charter. These details will also include procedures to ensure confidentiality and proper communication, the guidelines to be implemented by the DSMB and an outline of the content of the closed reports (unblinded) and open reports (blinded) that will be provided to the DSMB.

12. Changes from Analysis Planned in Protocol

There are no changes from the analysis planned in protocol.

13. Reference List

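### The protocol and SAP 4.2 define CGI-TS-I and CaGI-C as change from Week 4 to Week 12, which subtracts any drug effect already present at Week 4 and contradicts the SAP's own analysis text

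*SAP*

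**What the plan says.** The secondary endpoint lists in the protocol synopsis, Protocol 11.2 and SAP 4.2 give the same definition for both scales. Protocol 11.2 has "Change in Clinician Global Impression Tourette Syndrome of Improvement (CGI-TS-I) from Week 4 to Week 12" and SAP 4.2 has "Change in Caregiver Global Impression of Change (CaGI-C) from Week 4 to Week 12". The amendment rationale says that the starting point was moved to Week 4 because the scales are first given then. The same lists also ask for change in both scales from Baseline to Weeks 4, 6 and 8.

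SAP 8.2.4 prints the CaGI-C question: "how have the patient's symptoms changed (if at all) since the beginning of the study (before starting treatment". It is answered from 1 (very much improved) to 7 (very much worse). CGI-TS-I has the same 1 to 7 direction, and SAP 8.2.2 says "The improvement scale (CGI-TS-I) will be used at every visit after the Screening and Baseline Visits". The schedules of assessments show no Baseline rating for either scale.

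The SAP analysis text differs. Section 8.2.2 says "A secondary analysis will be performed on the CGI-TS-I at Week 12", while 8.2.4 says "A secondary analysis will be performed on the change in CaGI-C from Baseline to Week 12". The testing order in 8.2 has CaGI-C at Week 12 but CGI-TS-I from Baseline. SAP Section 12 states: "There are no changes from the analysis planned in protocol".

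**The concern.** A rating of improvement since before treatment is already a change score, so its Week 12 value is the 12-week result. Subtracting the Week 4 value treats it like a severity scale that needs a first measurement as its reference. But the first measurement here comes after four weeks on drug, with every weight band at its target dose by then. A child rated much improved (2) at both visits scores 0. So does a child rated no change (4) at both.

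The two scales are the second and fourth tests after the primary endpoint in the fixed sequence. If the definition is left open, whether a step passes could depend on which sentence is followed, and everything below a failed step becomes exploratory.

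**Working it through.** **1. The definitions side by side**

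| Place | CGI-TS-I | CaGI-C |
|---|---|---|
| Synopsis, Protocol 11.2, SAP 4.2: Week 12 | Week 12 minus Week 4 | Week 12 minus Week 4 |
| Same lists: Weeks 4, 6, 8 | from Baseline | from Baseline |
| SAP 8.2 testing order: Week 12 | from Baseline | score at Week 12 |
| SAP 8.2.2 and 8.2.4, headings | from Baseline | from Baseline |
| SAP 8.2.2 and 8.2.4, text | score at Week 12 | from Baseline |
| SAP 8.2.10 and 8.2.12, text | score at the visit | score at the visit |
| Baseline rating in the schedules | none | none |

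Only two of these can be computed as written: the score at the visit, and Week 12 minus Week 4. They are different quantities.

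**2. What each one estimates**

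Let E(t) be the drug-placebo difference in mean score at Week t. The Week 12 score estimates E(12). The listed endpoint estimates E(12) - E(4).

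**3. The plan's own power figure**

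Protocol 13.3 and SAP 3.5 give, for the primary endpoint, 75 per arm, difference 3, SD 6.1, alpha 0.05 (two-sided, per SAP Section 11) and 10% dropout.

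- Evaluable per arm: 75 x 0.9 = 67.5.
- Power = Φ(3 / (6.1 x √(2/67.5)) - 1.96) = Φ(2.857 - 1.96) = 81.5% (81.0% with the t distribution).

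The stated figure of over 80% is reproduced. The documents give no power, SD, between-visit correlation or time course for CGI-TS-I or CaGI-C.

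**4. Illustration for the two scales**

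Assumptions: the Week 12 score has the borrowed standardised effect d = 3/6.1 = 0.492; a fraction f of it is present at Week 4; the SD is equal at both visits; the between-visit correlation is ρ.

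- Expected effect of the difference score: d(1 - f).
- SD of the difference score, in units of the single-visit SD: √(2(1 - ρ)), which is 1.000, 0.894, 0.775 and 0.632 for ρ = 0.5, 0.6, 0.7 and 0.8.
- Power = Φ(2.857 x (1 - f) / √(2(1 - ρ)) - 1.96).

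| f | ρ = 0.5 | 0.6 | 0.7 | 0.8 |
|---|---|---|---|---|
| 0 | 81.5% | 89.1% | 95.8% | 99.5% |
| 0.25 | 57.3% | 66.9% | 79.0% | 92.3% |
| 0.50 | 29.8% | 35.8% | 45.4% | 61.7% |
| 0.75 | 10.6% | 12.3% | 15.0% | 20.3% |
| 1 | 5% | 5% | 5% | 5% |

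The last row is the two-sided type I error, since the expected difference is 0. The Week 12 score has 81.5% power in every row. The difference score has less power once f exceeds 1 - √(2(1 - ρ)), that is 0, 0.11, 0.23 and 0.37 for the four correlations.

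**The case against.** The strongest reply is that no analysis in SAP 8.2 subtracts the Week 4 score of either scale. Sections 8.2.2, 8.2.10 and the text of 8.2.12 use the score at the visit, and so does the CaGI-C entry in the testing order. The only entry there running from Week 4 to Week 12 is attached to CGI-TS-S, a separate matter. Protocol 13.2.1 also expects a Week 4 treatment difference for these scales, which would be meaningless if Week 4 were the subtracted reference. And a change from Baseline on a scale that already asks about change, modelled without a baseline covariate, can be read as loose wording for the score itself. All of this stands. It points to the Week 12 score as the likely intention, but it leaves the contradiction with SAP 4.2 and the protocol in place, and SAP Section 12 denies that one exists.

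A reader might infer that the fixed sequence is set up to fail at these steps. That holds only if the protocol and SAP 4.2 definition is the one applied; the testing order itself does not use it.

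A reader might also infer that the expected effect from Week 4 to Week 12 is near zero. The documents do not support that. In the earlier paediatric crossover study (Protocol 5.2.2.1) the treatment difference was -2.89 (SE 1.53) at Day 16 and -2.14 (SE 1.66) at Day 30. Those are YGTSS scores under a different dosing scheme, and neither difference was significant in the ITT population (p = 0.0664 and 0.2045). In the present trial every band but the lightest reaches its target dose only during Week 4. The dose on the evening before the Week 4 visit is withheld for PK sampling, and nothing in the documents shows what that does to the Week 4 rating.

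Finally, the pre-treatment reference is printed for CaGI-C only. For CGI-TS-I it is an inference, though a strong one: the first rating is at Week 4, with no earlier post-baseline rating to refer to.

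**Conclusion.** The definition in the synopsis, Protocol 11.2 and SAP 4.2 is wrong for a scale that rates change since before treatment, because it removes any effect present at Week 4. This follows from the printed question for CaGI-C and by inference for CGI-TS-I, and needs no numerical assumption. The documents also contradict each other on two endpoints in the fixed sequence, and the versions written as change from Baseline cannot be computed as differences.

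The size of the loss is open. It runs from none (82-99.5% power against 81.5%) if no effect is present at Week 4, through 30-62% power if half is present, to the 5% type I error if all is present. These figures rest on an effect size borrowed from the primary endpoint, 67.5 evaluable subjects per arm, and correlations of 0.5 to 0.8 that the documents do not give.

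**What to change.** In the protocol synopsis, Protocol 11.2 and SAP 4.2, 8.2, 8.2.2, 8.2.4 and 8.2.12, define the endpoints as the CGI-TS-I score and the CaGI-C score at Week 12, and at Weeks 4, 6 and 8 for the earlier time points. Remove the Week 4 and Baseline starting points for these two scales wherever they appear, including the section headings and the CGI-TS-I entries in the testing order. The CaGI-C entry in the testing order and SAP 8.2.10 already read this way. Record the change in SAP Section 12, and settle it before unblinding.

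The cost is a protocol clarification and SAP wording, with no new data or visits. Adjusting for baseline CGI-TS-S, which is collected, is an optional modelling choice and not part of this correction.

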4.3. Exploratory Endpoints

To evaluate the PK/pharmacodynamic relationship between plasma levels of ecopipam and treatment effect if possible.

5. Analysis Sets

5.1. Screened Set

The Screened Set will include all subjects screened. Unless specified otherwise, this set will be used for subject listings and for summaries of subject disposition.

5.2. Safety Set

The Safety Set (SS) will include all subjects who received at least one dose of study drug. The SS will be used for the analysis of the safety endpoints.

5.3. Modified Intent-to-Treat Set

The Modified Intention-to-Treat (mITT) set will include all randomized subjects who received at least one dose of study drug and have at least one post Baseline scoring of the YGTSS. The mITT set will be used for the analysis of primary and secondary efficacy endpoints. Subjects will be analyzed according to randomized treatment.

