For the Week 4 visit, a morning appointment is suggested. Parents/caregivers will be instructed not to administer the study medication to the subject on the evening prior to the Week 4 visit and to record the time of administration of the last dose of study medication taken. The study drug administration will occur on the day of the Week 4 visit at the site under the supervision of the study investigator. An intravenous catheter will be placed, and the subject will have samples collected at the following time windows: one sample at pre-dose (34 to 44 hours since the last dose), one sample between 0.5 and 1.5 hour after administration of study medication, and one sample between 2 and 4 hours after study drug administration. Any samples should be collected at least 30 min apart.

For the Week 12 visit, parents/caregivers will be asked to record the time of study drug administration on the evening prior to the visit. An appointment is suggested to be made for the morning of the Week 12 visit. A blood sample will be collected at the end of the visit. The time of sample collection will be recorded. Blood samples will be processed as outlined in the protocol and serum/plasma will be frozen, shipped and analyzed for ecopipam and SCH40853.

Statistical methods:

Efficacy:

The Modified Intention-to-Treat (mITT) population will include all randomized subjects who received at least one dose of study drug. The mITT population will be used for the analysis of the efficacy endpoints.

The primary efficacy endpoint for this study will be the change from Baseline (YGTSS-TTS from Baseline) to end of therapy (YGTSS-TTS from Week 12).

The primary endpoint will be assessed with a Mixed Model for Repeated Measures (MMRM) model which will include fixed effects for treatment, visit (categorical week in study), interaction between treatment and visit, center and a covariate for baseline YGTSS-TTS. Taking consideration of missing data, multiple imputation or tipping point method may be used as a sensitivity analysis

Secondary endpoints will be evaluated in a similar manner with hierarchy to preserve alpha.

Additional analyses may need to be conducted for data not collected at sites and/or collected via remote administration due to restrictions as a consequence of the COVID-19 pandemic or other qualifying event, details of these additional analyses will be specified in the SAP.

The full details will be specified in the SAP.

Safety:

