7.4. Dose Adjustment Criteria

Doses will be titrated up to and down from the target dose based on the subject's weight at Baseline according to the following weight bands to better achieve the targeted 2 mg/kg/day target dose: ≥ 18 to ≤ 23 kg, ≥ 23 to ≤ 34 kg, ≥ 34 to ≤ 44 kg, ≥ 44 to ≤ 68 kg, ≥ 68 to ≤ 83 kg, ≥ 83 kg. Those who cannot tolerate the target dose will be withdrawn from study. Weight band assignments will not change during the duration of the study. See Section 10.5 for direction on administration of study drug.

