13.1. Analysis Population

The Modified Intention-to-Treat (mITT) population will include all randomized subjects who received at least one dose of study drug and have at least one post Baseline scoring of the YGTSS. The mITT population will be used for the analysis of primary and secondary efficacy endpoints.

The Per-Protocol (PP) population will include subjects from mITT population who have no major protocol deviations. Before data are released for statistical analysis, a blinded review of all data will be performed by the Sponsor's clinical team to identify protocol deviations that may potentially affect the results. At this time, it will be determined if subjects and/or data should be excluded from the PP Population. The list of subjects or observations to be excluded from the PP Population, along with the reason for exclusion, will be finalized prior to database unblinding. Protocol deviations that occur due to COVID-19 related issues will be categorized separately as applicable.

The Safety population will include all subjects who received at least one dose of study drug. The safety population will be used for the analysis of the safety endpoints.

The Pharmacokinetics (PK) population will include all subjects from safety population who have a valid concentration measurement.

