3.3. Brief Description

This is a multicenter, placebo-controlled, double-blind, randomized, parallel-group, Phase 2b study in pediatric subjects (aged \geq 6 to <18 years) with TS. Following a Screening period up to 28 days and Baseline visit, eligible subjects will be randomized 1:1 to receive either a target steady-state dose of 2 mg/kg/day ecopipam HCl or matching placebo for a 4-week Titration period followed by an 8-week Treatment period. Following titration, subjects who weigh \geq 18 kg to \leq 23 kg will receive a 37.5-mg active dose (or placebo), subjects who weigh >23 kg to \leq 34 kg will receive a 50-mg active dose (or placebo), subjects who weigh >34 kg to \leq 44 kg will receive a 75-mg active dose (or placebo), subjects who weigh >44 kg to \leq 68 kg will receive a 100-mg active dose (or placebo), subjects who weigh >68 kg to \leq 83 kg will receive a 150-mg active dose (or placebo), and subjects who weigh >83 kg will receive a 200-mg active dose (or placebo).

After the Screening period, subjects will return to the clinic at Baseline and at 4, 6, 8, and 12 weeks after Randomization. Subjects will have telephone visits on Weeks 2 and 10 to assess adverse events and other safety parameters. Efficacy assessments will be conducted at Weeks 4, 6, 8, and 12 and safety assessments will be conducted at all visits as well. A Follow Up visit will be conducted in the clinic 7 and 14 days after the last dose of study medication. Subjects will also be contacted 30 days after the last dose of study medication to determine any adverse events. At study completion or early termination, subjects will be tapered off study drug as outlined in the protocol.

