8.1. Primary Efficacy Endpoint and Analysis

8.1.1. Primary Efficacy Analysis

The Yale Global Tic Severity Scale (YGTSS) is a clinician-completed rating scale used to quantify overall tic severity as well as specific subdomains of tic number, frequency, duration, intensity, and complexity. Each of these subdomains is scored, on a 5-point scale, separately for motor and vocal tics and then summed across both motor and vocal tics to yield a total tic score (TTS) ranging from 0 to 50. The YGTSS also provides for an overall impairment rating (0 = "none" to 50 = "severe"). The YGTSS has demonstrated acceptable internal consistency, good interrater reliability, and acceptable convergent and divergent validity.

YGTSS will be assessed at Screening, Baseline and at Weeks 4, 6, 8 and 12.

The primary efficacy endpoint for this trial will be the change from Baseline (score of YGTSS-TTS {i.e., sum of the motor and phonic tic scores} at Baseline) to end of therapy (score of YGTSS-TTS at Week 12). The analysis of primary efficacy endpoint will use the MITT set. Results for the PP set will also be provided.

Statistical analysis:

The primary endpoint will be analyzed with a Mixed Model for Repeated Measures (MMRM) model using the SAS MIXED procedure with REPEATED statement. The model will include fixed effects for treatment, visit, interaction between treatment and visit, region, age group (0 = children 6-11, 1 = adolescents 12-17) and covariate for baseline YGTSS-TTS.

If there is no sample size increase at the interim analysis, then a single MMRM based on all the data will be performed. However, if the sample size is increased from the planned (150) then two MMRM models will be performed and combined using the CHW (Cui-Hung-Wang) method, which controls the type 1 error, one MMRM model on the data from Stage 1 (the interim analysis data) and the second on data from Stage 2 (post-interim data). Information on treatment effect from the two stages will be combined in the weighted test-statistic:

$$T_{CHW} = \sqrt{\frac{n_1}{N}} T_1 + \sqrt{\frac{n_2}{N}} T_2$$

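### The mITT set is defined in two ways; the version the SAP uses leaves out dosed subjects who stop during titration and miss the Early Termination YGTSS, a probably small bias towards ecopipam

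*SAP*

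**What the plan says.** The protocol synopsis (Statistical methods) states: "The Modified Intention-to-Treat (mITT) population will include all randomized subjects who received at least one dose of study drug". It adds no further condition. Protocol 13.1 requires in addition that subjects "have at least one post Baseline scoring of the YGTSS". SAP 5.3 follows 13.1: "all randomized subjects who received at least one dose of study drug and have at least one post Baseline scoring of the YGTSS". SAP 4.1.1 writes the same condition into the target population of the primary estimand. SAP section 12 reports no changes from the protocol.

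On timing, SAP 8.1.1 says "YGTSS will be assessed at Screening, Baseline and at Weeks 4, 6, 8 and 12". Week 4 is the end of the 4-week titration. Before it there is only a telephone contact without a YGTSS: "Subjects will have telephone visits on Weeks 2 and 10 to assess adverse events and other safety parameters" (SAP 3.3).

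On early stopping, Protocol 7.4 says "Those who cannot tolerate the target dose will be withdrawn from study". Protocol 10.5 and SAP 3.7 likewise discontinue subjects who do not tolerate titration. The schedule of assessments places a YGTSS in the Completion/Early Termination column. Protocol 7.5 expects all discontinuing subjects to complete the early discontinuation procedures; Protocol 8.3 asks for them where this is feasible.

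**The concern.** Membership of mITT depends on something observed after randomization. A child who takes study drug, stops in Weeks 1 to 4 and does not attend the exit visit has no post-baseline YGTSS and is removed from the set. If such losses are more frequent on ecopipam, the comparison is made among subjects partly selected by tolerability.

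This also works against the SAP's own rules. SAP 4.1.1 assigns placebo-based imputation to discontinuation for treatment-related adverse events when Week 12 is missing, yet its target population leaves out the earliest of those cases. SAP 8.2.6 classes any subject without a response as a non-responder, but these subjects are taken out of the denominator before that rule applies. No other planned efficacy analysis brings them back.

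**Working it through.** **1. The plan's own figure.** Inputs from Protocol 13.3 and SAP 3.5: 75 per arm, difference 3, SD 6.1, two-sided alpha 0.05, 10% dropout. Evaluable per arm: 75 × 0.90 = 67.5. Standard error: 6.1 × √(2/67.5) = 1.050. Then 3/1.050 − 1.960 = 0.897, which gives power of 81.5%. The stated figure of more than 80% reproduces and is not in question here.

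**2. Who can be lost.**
- Stops before Week 4, exit YGTSS obtained: has a post-baseline score and stays in mITT.
- Stops before Week 4, exit YGTSS missed: no post-baseline score, so outside mITT under Protocol 13.1 and SAP 5.3 but inside it under the synopsis.
- Stops after Week 4 with a Week 4 score: stays in mITT.

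Only the second group is affected.

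**3. Which analyses they leave.**
- Primary and secondary efficacy analyses: mITT (SAP 5.3 and section 8).
- Missing-data sensitivity analyses: mITT (SAP 8.1.2).
- Per-protocol set: a subset of mITT (SAP 5.4).
- Estimand target population: mITT (SAP 4.1.1).

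No efficacy analysis covers all randomized and dosed subjects.

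**4. How many.** The documents give no rate of titration failure without an exit score. The closest source is the earlier paediatric crossover study, which gave four weeks of treatment: one subject of 40 discontinued for an adverse event on ecopipam (Protocol 5.3.1), and 38 of 40 completed (Protocol 5.3.2). By assumption, 1/40 × 75 = 1.9, or about 2 ecopipam subjects, none with an exit score. One placebo subject is added, also by assumption. A second case takes 3 and 1.

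**5. Effect on a responder endpoint.** The responder counts, 36 on ecopipam and 24 on placebo, are assumed for illustration. Every lost subject is counted as a non-responder.

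| Set | Ecopipam | Placebo | Difference | Odds ratio |
|---|---|---|---|---|
| All dosed | 36/75 = 48.0% | 24/75 = 32.0% | 16.0 points | (36/39)/(24/51) = 1.96 |
| 2 and 1 lost | 36/73 = 49.3% | 24/74 = 32.4% | 16.9 points | (36/37)/(24/50) = 2.03 |
| 3 and 1 lost | 36/72 = 50.0% | 24/74 = 32.4% | 17.6 points | (36/36)/(24/50) = 2.08 |

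**6. Effect on a placebo-based imputation.** Suppose the retained ecopipam subjects gain 3 points over placebo and k lost ones gain nothing. The arm-level effect is 3 × (75 − k)/75: 2.92 for k = 2 and 2.88 for k = 3. This isolates the contribution of the lost subjects. Jump-to-reference within mITT already imputes later dropouts as placebo, so the planned estimate would itself start below 3.0.

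**7. Observed-data MMRM.** A subject with no post-baseline score contributes no response record, so this model gives the same result under either definition.

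**The case against.** The strongest reply is that the plan already provides for these subjects. A YGTSS is scheduled at Early Termination, all who discontinue are expected to attend, titration failures stay in contact while tapering off drug, and remote assessment is allowed in qualifying circumstances. A titration failure should therefore normally have a post-baseline score. The tipping-point code in SAP 14.5 even has a branch for subjects whose first missing visit is Week 4. SAP 7.1 will summarize and list those left out of each analysis set with reasons, so an imbalance would be visible. The protocol body and the SAP agree, and the synopsis defers to the SAP for full details, so the operative definition is clear. The 25%, 50% and 75% responder endpoints and complete remission come only sixth and seventh after the primary in the fixed sequence.

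Most of this stands, and it limits the size of the problem. A reader might infer that titration works as a hidden run-in that removes intolerant children from the ecopipam arm as a group. The documents do not support that: only those who also miss the exit visit are lost, and the missing-data analyses can still include early dropouts who have an exit score. A reader might also infer that the SAP departs from the protocol; in fact the conflict lies within the protocol, between the synopsis and 13.1.

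Two things remain. The exit visit is expected but not assured. And a listing of excluded subjects discloses the loss without correcting the estimates.

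**Conclusion.** The inconsistency is real, and the narrower definition can remove dosed subjects from every efficacy analysis after randomization, contrary to the purpose of SAP 4.1.1 and 8.2.6. It should be corrected, but it does not undermine the observed-data primary MMRM.

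The direction is inferred. It favours ecopipam if early intolerance is more frequent on active drug and those subjects gain little. Protocol 5.3.1 makes this plausible, since adverse events in the earlier paediatric study were more common on ecopipam.

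The likely size is about 1 to 2 percentage points on a responder difference (16.0 to 16.9 or 17.6) and 0.07 to 0.12 on the odds ratio (1.96 to 2.03 or 2.08). These figures rest on the assumed responder counts, on 2 to 3 ecopipam subjects and 1 placebo subject lost, and on none of them having an exit score. A reader might suppose much larger losses. The adult open-label study had 3 of 18 discontinue study drug for an adverse event, but at adult doses over eight weeks, and that figure says nothing about missed exit assessments. The plan allows for 10% of 150, or 15 dropouts, for all reasons over the whole study, so a heavy loss confined to titration and without exit scores has no basis in the documents.

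**What to change.** Use the synopsis definition (randomized, at least one dose, analysed as randomized) in Protocol 13.1, SAP 5.3 and the SAP 4.1.1 target population. State in SAP 8.2.6 and 8.2.7 that subjects without a post-baseline YGTSS count as non-responders. Include these subjects in the SAP 8.1.2 imputation analyses. It would also help to say which visit an Early Termination YGTSS taken during titration is analysed under, because SAP 6.1 uses nominal visits, SAP 6.4 applies no windows, and the schedule puts that assessment in the Week 12 column.

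The sponsor should settle one consequence at the same time. SAP 8.1.2 describes the primary analysis as an MMRM on observed data, which the change leaves as it is. If the placebo-based imputation in SAP 4.1.1 is applied in the primary analysis, that result will include these subjects too and can change.

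The cost is wording in the protocol and SAP, with no new data and no change to dosing or withdrawal rules. The responder and sensitivity estimates will probably be slightly less favourable to ecopipam.
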